STUDY PROTOCOL AND STATISTICAL ANALYSIS PLAN

Official title: Problem-Solving Training for Care Partners of Adults with Traumatic Brain Injury

NCT number: NCT03739450

IRB approved date: 06-02-20

**The University of Texas Southwestern Medical Center at Dallas
Institutional Review Board**

Protocol Template (for Investigator Initiated Studies)

Title: Problem-Solving Training for Care Partners of Adults with Traumatic Brain Injury

1. Introduction and Purpose: The purpose of this project is to:

AIM 1: Assess the feasibility of delivering up to 6 sessions of Problem Solving Training (PST) to care partners of individuals with traumatic brain injuries (TBI) during the inpatient rehabilitation stay.

- **Hypothesis 1a:** Care partners will complete at least three intervention sessions (in person and/or via telephone) prior to discharge from inpatient rehabilitation and will report high satisfaction.
- **Aim1a:** Determine the number of sessions that it is feasible to complete during the inpatient rehabilitation stay and factors associated with non-compliance.

AIM 2: Assess the efficacy of PST plus TBI-specific education compared to TBI-specific education alone for improving the outcomes of care partners of individuals with TBI.

- **Hypothesis 2a:** PST will reduce care partners' burden and depressive symptoms (primary), while improving care partners' coping skills (secondary) at one-month post discharge more than TBI-specific education alone.
- **Hypothesis 2b:** Effects of the PST intervention on care partner burden, depressive symptoms, and coping will be maintained at 6 months post-intervention.

2. Background: The chronic consequences of TBI are recognized, but ongoing support for adults with TBI living in the community is limited. This puts undue burden on care partners, particularly during the transition from hospital to home. It often leads to adverse consequences among care partners, such as emotional distress and increased substance abuse.^{1,2} Care partners of individuals with TBI often experience high levels of burden, which may result in depression, anxiety, increased somatic symptoms, and reduced quality of life.^{1,3,4} Care partner burden is largely predicted by the extent to which care partners' perceived needs are met.^{1,5,6} As the consequences of TBI continue to change over time, so too do the perceived needs of care partners.⁷⁻¹¹ One study suggests that only 55% of care partner needs are perceived as being met.¹² A systematic review of qualitative studies for care partners of adults with stroke revealed seven themes with regard to experiences, needs, and preferences of care partners during inpatient rehabilitation.¹³ Care partners expressed a desire to be included, informed, and recognized as a stakeholder in recovery, the need to navigate an alien culture and environment, and the need to manage the transition home.¹³ The authors concluded that "we need to make deliberate efforts to provide a more inclusive environment that better supports and prepares carers for their new role".¹³ Despite this established need during inpatient rehabilitation, there are currently no evidence-based interventions for care partners of adults with TBI to prepare them for their new role prior to discharge of care recipients from inpatient rehabilitation. Hence, there is a critical need to provide care partners of individuals with TBI with the necessary skills to navigate this difficult transition from hospital to home.¹⁴ Self-management training for care partners of adults with other chronic conditions demonstrates strong potential for application to care partners of adults with TBI.

Problem-Solving Training (PST) is an evidence-based, self-management approach that teaches a simple, systematic method for evaluating problems, generating and selecting solutions, creating and implementing realistic goals and action plans, and evaluating whether those plans effectively addressed the specific goal.^{15,16} A growing body of evidence indicates that PST post-discharge is associated with reduced distress among care partners of adults with TBI.¹⁷⁻¹⁹ Problems previously seen as overwhelming are regarded as solvable and manageable when approached in a stepwise

fashion using PST, thereby reducing perceived burden and emotional distress. PST empowers care partners to be active participants in directing health and rehabilitation services.

We anticipate that care partners will be able to complete a minimum of 3 sessions during the inpatient rehabilitation stay, with the goal of completing 6 sessions. We also anticipate that PST + Education will be more effective than Education alone for reducing caregiver burden and depressive symptoms and improving positive coping among care partners. This study will provide evidence for effective strategies to support and improve outcomes for care partners during the transition from hospital to home. This will benefit the TBIMS as a whole by providing an evidence-based and feasible intervention for care partners, upon whom the TBIMS relies heavily for participant enrollment and data collection, in addition to the ongoing support that care partners provide to the primary beneficiaries of TBIMS services, individuals with TBI. PST is an evidence-based, self-management approach with a strong theoretical foundation that has demonstrated efficacy for care partners of individuals with disabilities. Early work indicates that it is also effective for care partners of adults with TBI. However, there are no studies evaluating whether delivery of PST to care partners is feasible and effective during inpatient rehabilitation. The proposed project builds upon this foundation of evidence to address this critical gap in the literature.

3. Concise Summary of Project: Participants are care partners of adults with TBI who are inpatient patients at Zale Lipshy Hospital or Parkland Memorial Hospital. They will complete baseline testing and follow-up testing at 1-month and 6-months post-intervention. They will participate in up to 6 sessions of the Problem Solving Training intervention, delivered in person or via telephone. These data will be used to assess the feasibility of delivering this intervention. These data will also be used for secondary analysis to determine relationships between baseline measures, demographics, and outcomes among care partners of adults with traumatic brain injuries.

4. Study Procedures: This will be a randomized controlled trial, with blocked randomization stratified by performance site, of PST + Education vs Education alone for care partners of adults with TBI admitted to inpatient rehabilitation. Baseline assessment and all intervention sessions will occur during the time the patient with TBI is in inpatient rehabilitation, with the exception of the last intervention session, which can occur via telephone post-discharge. Follow-up assessments will occur at 1-month and 6-months after the completion of the intervention.

Description of Interventions: Care partners in the intervention group will receive PST training in addition to TBI-specific education. Participants in the Control group will receive TBI-specific education alone. Both groups will receive up to 6 sessions, delivered in person or via telephone. Trained members of the research team with master's level education or equivalent experience will provide both interventions using a specific curriculum that has been validated in our previous research studies. These activities will take place prior to discharge from inpatient rehabilitation. Sessions will occur face-to-face whenever possible and over the telephone circumstances when face-to-face is not feasible. Up to 6 sessions will be delivered, with a target of 2/week, maximizing the likelihood of completing all sessions before discharge and providing sufficient time for care partners to put their plans into action between sessions. Sessions will conclude at discharge, with the exception of completing the final session via telephone if it was not completed prior to discharge. We will audio record the delivery of the sessions to ensure fidelity and evaluate feasibility, and document completion, reasons for non-compliance/non-completion, method of delivery, session length, participant engagement, and a brief summary of the PST steps covered during each session.

A trained research staff, blinded to intervention allocation, will perform all assessments in person, via telephone, or will send the assessments electronically to the participant through RedCap at baseline, 1-month, and 6-months post-intervention. Blinding will be ensured by allocating to group assignment after baseline assessment is complete, having different staff performing assessments vs delivering

the intervention, scheduling meetings with assessors and interventionists separately, and instructing participants to not discuss the intervention with the person calling to complete follow-up assessments. We will collect data on demographic (age, gender, race, ethnicity, education), care partners relationship information (nature, duration, living status), and outcome measures assessing mood, caregiver burden, coping skills, self-efficacy, and satisfaction with the intervention (data collection forms for each assessment time point are attached in a later section).

5. Sub-Study Procedures: n/a

6. Criteria for Inclusion of Subjects:

1. Identified as care partner of an individual with TBI admitted to inpatient rehabilitation. A care partner is defined as an individual (spouse, partner, family member, friends, or neighbor) involved in assisting the patient with activities of daily living and/or medical tasks or responsible in any way for the patient's well-being after discharge from inpatient rehabilitation.
2. >1-year relationship
3. Ability to communicate in English.
4. >18 years old
5. Capacity to self-consent

7. Criteria for Exclusion of Subjects:

1. Dispute over care partner's role in the care of patient.
2. Failure to meet all inclusion criteria.

8. Sources of Research Material: Participant-completed surveys/questionnaires. Members of the research team will record all data collected (demographic data, care partner relationship information, session-specific information, and outcome measures) on study forms. Paper forms will be kept in locked filing cabinets and data will be entered directly into an electronic database managed by the TBI Model Systems National Data and Statistical Center that meets standards required by UTSW. Assessment data may also be captured through secure RedCap. Intervention sessions will be audio-recorded for the purpose of monitoring intervention fidelity.

9. Recruitment Methods and Consenting Process: Participants will be willing care partners of individuals with TBI at either Zale Lipshy University Hospital, Parkland Memorial Hospital Centers, or Baylor Scott and White Rehabilitation Institute. Care partners of patients screened for the TBI Model Systems (STU 082010-092) studies will be approached about participation or given a flyer by the research coordinator for those studies. No screening for eligibility/screening for patients is necessary. We will not review/collect any PHI. Study staff will recruit care partners as close as possible to admission of the patient with TBI into acute or inpatient rehabilitation, to maximize the likelihood of completing PST training prior to discharge. Study staff will approach care partners in a private setting, such as the patient's room or private office, or via telephone to discuss the purpose of the project and to obtain informed consent. Additionally, study staff will fully explain all study procedures and will answer all questions regarding the project. Care partner participants who agree to be part of the study will then sign an IRB-approved consent form. The informed consent forms will include contact information for the IRB and the PI, who may be contacted at any time with questions or concerns. Participants will be given a subject ID, which will be used to refer to the participant on all research documents.

10. Potential Risks: The proposed study involves minimal risk to participants. There is always a risk of a breach of confidentiality of personal information and associated privacy of participants. The baseline screening, problem-solving therapy sessions, and follow up data collection visits may produce discomfort or anxiety secondary to the discussion of emotionally laden topics. Questionnaire

items assess sensitive topics, including substance use, coping, depression, caregiver burden, and satisfaction with health-related services.

11. Subject Safety and Data Monitoring: A detailed Data and Safety Monitoring Plan will be submitted to the IRB. The study staff (PI, Co-Investigators, research coordinator, interventionist) will be responsible for collecting and recording all data. As results are collected, all Adverse Events will be identified, graded for severity and assigned causality, reported to the required entities, and compiled for periodic review. After assigning causality, the PI will decide the course of action for the study participant. The PI will evaluate all Adverse Events and determine whether the Adverse Event affects the risk/benefit ratio of the study and whether modifications to the protocol or informed consent form are required. Throughout this process, the PI will inform and collaborate with the research team. The plan to monitor participant data and safety will specifically include the following: (1) [name] will inspect collected data; (2) The IRB offices will be contacted if there is an Adverse Event due to participation; (3) the research protocol will be revised if it is determined that the protocol or intervention presents an unforeseen risk to participants; (4) if an event occurs that requires immediate attention and [name] is unavailable, then members of the research team will follow the emergency procedures put in place by the research team, which may include calling emergency medical services. [name] will develop procedures for all data management functions including data quality checks and verification, in collaboration with the TBI Model Systems National Data and Statistical Center. Internal edit and logic checks (e.g., out of range values, internal inconsistencies) will be developed and run quarterly. Descriptive statistics will be calculated and included into quarterly reports to ensure the quality of data and progress of the study.

12. Procedures to Maintain Confidentiality: In order to assure participant confidentiality, all participants will be assigned a unique study identification number. Links to identifiers will be maintained at UTSW by study staff. All databases will use the subject ID number rather than private health information. The only exception will be that the RedCap database will include the participant e-mails and information necessary to obtain eConsents. This is necessary in order to send out the assessments via RedCap and to obtain participant consent through RedCap. PHI in RedCap will be marked as patient health information, for which only study personnel will have access. Signed consent forms and all paper study documents will be maintained by the PI and co-investigators at participating centers behind a locked door in a locked file cabinet or in RedCap.

13. Potential Benefits: Participants receiving the PST intervention may benefit from reduced symptoms of burden and depression and improvements in adaptive coping. Participants receiving Education may also benefit from reduced symptoms or greater self-efficacy. Further, from this study, we hope to improve clinical programming to better support care partners of patients in acute hospitalization and inpatient rehabilitation. This could lead to improving not only the long-term health and well-being of care partners, but also of individuals with acquired disabilities.

14. Biostatistics: Specific Aim 1: The primary outcome is the total number of sessions completed prior to discharge, with a threshold of 80% of participants completing a minimum of 3 sessions as an indicator of feasibility. We will descriptively present reasons for non-compliance and explore factors associated with non-compliance (e.g. demographics, hospital length of stay, etc.). The secondary outcome for feasibility is satisfaction, with an item mean of ≥ 3.5 on the CSQ-8 as an indicator of high satisfaction. **Specific Aim 2:** To test our first hypothesis, we will use intent-to-treat analyses to measure the pre-post-test differences in each outcome between baseline and 1-month follow-up using a paired t-test or Wilcoxon signed rank test as appropriate. To address our second hypothesis, we will use intent-to-treat analyses to measure the pre-post-test differences in each outcome between baseline and 6-month follow-up (all participants) using paired t-tests or Wilcoxon signed rank tests. Effect sizes will be calculated and interpreted as follows: <0.2 =no/minimal effect; $0.2-0.5$ = small effect; $0.5-0.8$ =medium effect; ≥ 0.8 =large effect.

References

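### Hypothesis 2b says PST effects are maintained at 6 months, but its only test is baseline versus 6 months, which compares neither the arms nor the two follow-ups

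*Combined protocol and SAP*

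**What the plan says.** Section 1 sets Aim 2 as a comparison of arms: "Assess the efficacy of PST plus TBI-specific education compared to TBI-specific education alone". Hypothesis 2a places the first effect "at one-month post discharge more than TBI-specific education alone". Hypothesis 2b then reads: "Effects of the PST intervention on care partner burden, depressive symptoms, and coping will be maintained at 6 months post-intervention".

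Section 4 describes the design: "This will be a randomized controlled trial, with blocked randomization stratified by performance site, of PST + Education vs Education alone". On timing it says "Baseline assessment and all intervention sessions will occur during the time the patient with TBI is in inpatient rehabilitation", apart from a last session that may be held by telephone after discharge, and "Follow-up assessments will occur at 1-month and 6-months after the completion of the intervention".

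For the second hypothesis, Section 14 (Biostatistics, Specific Aim 2) gives one analysis. It is to "measure the pre-post-test differences in each outcome between baseline and 6-month follow-up (all participants", using paired t-tests or Wilcoxon signed rank tests under intent-to-treat. The 1-month analysis is also paired against baseline. Effect sizes will be computed and graded by cut-offs, but the section does not say which contrast they describe. There is no test between arms, no arm-by-visit term, no contrast of 1 month with 6 months, and no definition of what counts as maintained.

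**The concern.** A statement that a treatment effect is maintained has two parts. There is a difference between treated and control participants, and that difference persists from an earlier visit to a later one. The test in Section 14 addresses neither. It asks whether scores at 6 months differ from scores taken while the patient was an inpatient.

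The protocol itself gives reasons why scores may move for causes other than PST. Section 2 says: "As the consequences of TBI continue to change over time, so too do the perceived needs of care partners". It also singles out the move from hospital to home as a time of particular burden. Section 13 allows that Education participants may improve too.

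The error can go either way. If both arms improve alike, the test may suggest a maintained PST effect when PST has no advantage left. If care partners find life harder after discharge and PST protects them, PST scores may stay near baseline and a real, kept advantage would not be seen.

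**Working it through.** There is no figure in the plan to reproduce. The documents give no sample size, significance level, SD, Aim 2 target effect or margin for maintenance. The mismatch follows from the wording; the numbers below only show how the planned test behaves under stated assumptions.

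**Hypothesis and test side by side**

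| Needed for 2b | Given in Section 14 |
|---|---|
| PST + Education against Education alone | Paired test, which has no arm term |
| 6-month effect set against 1-month effect | 6 months against baseline only |
| A meaning for *maintained* | None |

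The reference to all participants could mean one pooled test or a test in each arm. The mismatch is the same under both readings.

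**Illustration 1: no PST advantage at 6 months, both arms improved equally**

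Assumptions: SD 1 at each visit, baseline-to-follow-up correlation r = 0.5, two-sided 5%, common improvement d of 0.5 or 0.3 SD.

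- SD of change = √(2(1 − r)) = √(2 × 0.5) = 1.
- Noncentrality = (d / SD of change) × √n, with n − 1 degrees of freedom.
- Example, d = 0.5 and n = 20: 0.5 × √20 = 2.236; critical t on 19 df = 2.093; power 0.56.

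| Pairs | d = 0.5 | d = 0.3 |
|---|---|---|
| 20 | 0.56 | 0.25 |
| 30 | 0.75 | 0.36 |
| 60 | 0.97 | 0.63 |

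Only the common 6-month change enters this formula. The 1-month difference does not appear, so the table measures the missing arm comparison and nothing else. In simulation (20,000 trials per scenario, 30 or 50 per arm, r = 0.5 or 0.7), a between-arm test of 6-month change favoured PST in about 2.4% to 2.7% of trials when both arms improved by 0.5 SD, as expected for one tail of a two-sided 5% test.

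**Illustration 2: advantage fully kept, but Education worsens**

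Same simulation settings. Education is 0.5 SD worse than baseline and PST is unchanged at both visits, a constant advantage of 0.5 SD. The pooled paired test is favourable in about 0% of trials and the PST-arm paired test in 2% to 3%. The between-arm test favours PST in 48% to 90%.

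**Illustration 3: advantage halves between visits**

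The PST advantage is 0.8 SD at 1 month and 0.4 SD at 6 months, with Education unchanged. The PST-arm paired test at 6 months is significant in 56% to 95% of trials, and the between-arm test at 6 months in 33% to 72%. Neither says that half of the benefit has gone. Only the change in the between-arm difference addresses that.

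**The case against.** The strongest objection is that the harm comes almost entirely from having no comparison of arms. Much of this stands. The probabilities in illustration 1 would be identical had PST never worked, and a between-arm test at 6 months brings that error down to its nominal level. A reader might infer that those figures measure loss of effect between 1 and 6 months going undetected; they do not. What remains distinct is that even a 6-month arm comparison would leave open how much of the 1-month benefit was kept.

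Second, *maintained* can fairly be read as still present at 6 months. On that reading a between-arm estimate at 6 months answers 2b and no 1-month significance is needed first. This also stands, and the fix allows for it. The paired test fails on that reading too.

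Third, Section 14 calculates effect sizes and uses the same baseline at both follow-ups, so some descriptive comparison of visits is possible. That is true, but the contrast is unstated, and nothing is planned that compares visits between arms.

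A reader might also infer that change from baseline to 6 months would mostly reflect the course from hospital to home. The documents do not support that: Section 2 says needs change but gives no symptom course, and its remark on the transition home does not point to natural easing. All that can be said is that such change may contribute. Nor does the plan commit to calling an effect maintained whenever the paired test is significant; it states no decision rule at all.

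**Conclusion.** The concern holds. The 2b test cannot support or refute the hypothesis it is assigned to, because it compares neither the arms nor the two follow-ups. Naming intent-to-treat does not change this: it settles who is analysed, not what is compared. Since the 1-month analysis is also paired against baseline, the plan does not test a between-arm effect at 1 month that could later be maintained.

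This conclusion rests on the wording of Sections 1 and 14 and needs no numerical assumption. The size does need assumptions. With no PST advantage at 6 months and r = 0.5, the chance of a significant paired result runs from 0.25 (20 pairs, 0.3 SD common improvement) to 0.97 (60 pairs, 0.5 SD). The amount of common change in this population is unknown from the documents and could be in either direction. The point should be corrected before analysis; it does not call the trial's design or data collection into question.

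**What to change.** In Section 14, replace the 2b test with a between-arm analysis of the 1-month and 6-month scores. One suitable form is a baseline-adjusted mixed model with arm, visit, arm-by-visit and site. For each outcome, report the PST-minus-Education difference with its 95% CI at 1 month, at 6 months, and for the change from 1 to 6 months.

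Then fix the wording of conclusions in advance:

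- State that an effect is present at 6 months if the 6-month CI excludes zero in favour of PST, whether or not the 1-month test was significant.
- Base any statement on how much of the 1-month benefit was kept on the 1-to-6-month change and its CI, not on significance at 6 months alone.

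A rule that called the effect maintained when both visits are significant would not do. Simulated with 30 to 50 per arm and r of 0.5 to 0.7, it passes a benefit that halves from 0.8 to 0.4 SD in about 32% to 73% of trials, and a fully kept 0.5 SD benefit in only about 31% to 82%.

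The cost is SAP wording and one added contrast on data already collected. The downsides are that 2b becomes harder to claim and that the CI for the change may be wide. Under the same assumptions, and using unadjusted scores, its half-width is about 1.96 × √(2(1 − r)) × √(2/n) with n per arm. That is 0.51 SD for n = 30 and r = 0.5, and 0.30 SD for n = 50 and r = 0.7.

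### Aim 2 asks whether PST beats education, but the planned paired tests compare neither arms nor randomisation sites

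*Combined protocol and SAP*

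**What the plan says.** **The question.** Aim 2 in Section 1 is comparative: "Assess the efficacy of PST plus TBI-specific education compared to TBI-specific education alone". Hypothesis 2a predicts that PST will improve burden and depressive symptoms (primary) and coping (secondary) "at one-month post discharge more than TBI-specific education alone". Hypothesis 2b concerns whether those effects last to 6 months.

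**The design.** Section 4 sets up a randomised controlled trial "of PST + Education vs Education alone for care partners of adults with TBI admitted to inpatient rehabilitation", "with blocked randomization stratified by performance site".

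**The analysis.** Section 14 is the only place that gives an Aim 2 analysis. At 1 month, the change from baseline in each outcome is assessed "using a paired t-test or Wilcoxon signed rank test as appropriate". At 6 months, the change is assessed "between baseline and 6-month follow-up (all participants) using paired t-tests or Wilcoxon signed rank tests". Both are labelled intent-to-treat. Effect sizes will be calculated and graded by bands, but the text does not say whether they are within or between arms. No two-sample test, regression, arm term or site term is given.

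**The sites.** Section 3 describes care partners of patients "who are inpatient patients at Zale Lipshy Hospital or Parkland Memorial Hospital". Section 9 recruits at "Zale Lipshy University Hospital, Parkland Memorial Hospital Centers, or Baylor Scott and White Rehabilitation Institute". Performance site is not defined.

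**The concern.** A paired test has as its null hypothesis that the mean (or median) change is zero. Hypothesis 2a concerns a different quantity, the difference in change between two randomised arms. A plan followed to the letter could report significant improvement when PST adds nothing to education.

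A shared change is plausible here. Baseline is taken during the inpatient stay and follow-up comes after it. Both arms receive up to six sessions, and Section 13 expects that education may itself reduce symptoms. Randomisation is what separates PST from these influences, and the planned tests do not use it.

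Site is a secondary matter. When randomisation is balanced within site, an arm comparison that ignores site has a standard error that is too wide to the extent that site predicts outcome after allowing for baseline. The documents do not say whether it does.

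**Working it through.** The documents give no sample size, alpha, power, SD, allocation ratio or expected change for Aim 2, so there is no planned figure to reproduce. The check has three parts; the inputs to parts 2 and 3 are assumptions.

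**1. What the paired test estimates.** Let the mean change be *c* with education alone and *c* + δ with PST. Hypothesis 2a is about δ. With 1:1 allocation (assumed):

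- paired test on everyone: null hypothesis *c* + δ/2 = 0;
- paired test in the PST arm: null hypothesis *c* + δ = 0;
- neither is δ = 0.

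The mismatch runs both ways. If δ = 0 and *c* ≠ 0, the tests reject with no PST effect. If the education arm worsens by 0.3 SD and PST does 0.6 SD better, the pooled mean change is −0.3 + 0.6/2 = 0, and the pooled test misses a real benefit.

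**2. How often the paired test is significant when δ = 0.** Assumed: two-sided 5% test; both arms change by *d* SDs of the change score; 25, 50 or 75 per arm with complete follow-up. Power comes from the noncentral *t* distribution with *n* − 1 degrees of freedom and noncentrality *d*√*n*. For example, *d* = 0.2 and 100 participants give 0.2 × √100 = 2.0 and power 0.508. If the test is run in each arm, with power *p* in each, the chance that PST is significant and education is not is *p*(1 − *p*).

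| Shared change | Paired test on everyone (n = 50, 100, 150) | One arm, *p* (n = 25, 50, 75) | *p*(1 − *p*) |
|---|---|---|---|
| 0.1 SD | 0.107, 0.168, 0.230 | 0.077, 0.107, 0.137 | 0.071, 0.095, 0.118 |
| 0.2 SD | 0.284, 0.508, 0.682 | 0.161, 0.284, 0.401 | 0.135, 0.203, 0.240 |
| 0.3 SD | 0.548, 0.844, 0.954 | 0.302, 0.548, 0.727 | 0.211, 0.248, 0.198 |

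A separate simulation (4,000 trials per case, three sites, shared change 0.3 SD, no site effect) agrees. At 30 and 60 per arm the pooled paired test was significant in 62.5% and 91.0% of trials. A two-sample test of change was significant in 4.8% and 5.0%.

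**3. What omitting site would cost in an arm comparison.** Let *s* be the share of variance left after baseline that site explains. With arms balanced within site, the standard error without site is too wide by the factor *f* = 1/√(1 − *s*). For a comparison with 80% power when site is included (two-sided 5%), power without site is Φ(1.960 + 0.842 − 1.960*f*), and type I error is 2Φ(−1.960*f*).

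| *s* | *f* | Power without site | Type I error without site |
|---|---|---|---|
| 0 | 1.000 | 0.800 | 0.050 |
| 0.02 | 1.010 | 0.794 | 0.048 |
| 0.05 | 1.026 | 0.785 | 0.044 |
| 0.10 | 1.054 | 0.769 | 0.039 |

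Simulation with 50 per arm, blocks of 4 within two or three sites and 6,000 trials per case gave standard-error ratios of 1.000 at *s* = 0, 1.026 at *s* = 0.05, and 1.054 to 1.055 at *s* = 0.10. With no site effect, including site changed the mean standard error by less than 0.1%.

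A stronger site effect costs more. In the 4,000-trial simulation, three equal sites shifted by −0.6, 0 and 0.6 SD have between-site variance 0.6² × 2/3 = 0.24, so *s* = 0.24/1.24 = 19%. For a true 0.5 SD difference, power without and with site was then 40% and 49% at 30 per arm, and 70% and 77% at 60 per arm.

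**The case against.** The best defence is that an arm comparison was intended and loosely written. Section 14 says its analyses test the stated hypotheses, calls them intent-to-treat, and promises effect sizes that could be between arms. This supports intention only. Intent-to-treat settles who is analysed and in which arm, and the effect-size sentence defines no contrast, test or interval. The fair statement is that the plan contains no defined estimate or test of the arm difference.

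The phrase about all participants is ambiguous, and this stands. It appears only for 6 months and may mean the intent-to-treat set rather than pooled arms. The paired tests could also be run separately in each arm or site. That would not repair the plan: one significant and one non-significant within-arm result is not a test of their difference, and the last column of the first table shows how often that pattern arises by chance.

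The assumed shared change drives the size. At 0.05 SD the pooled test is significant in only 6–9% of trials, and PST alone reaches significance in 5–7%. The documents support no particular value.

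Finally, the site term taken alone is a modest improvement, and the differing hospital lists are a consistency point, not evidence about the tests. Both are correct. They belong here because the repaired model needs defined site levels.

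**Conclusion.** The concern holds. Aim 2 and Hypothesis 2a ask a between-arm question of a randomised trial, and Section 14 answers it with tests of change from baseline that cannot contrast arms. This is an incorrect specification, not a missing detail: carried out exactly, it can support an efficacy claim when both arms change equally.

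The missing arm comparison is the main problem. How often it misleads depends on the assumed shared change and arm size, from little above 5% at 0.05 SD to about 95% for the pooled test at 0.3 SD and 75 per arm. The missing site term is small: it errs on the conservative side, costs nothing without a site effect, and costs about 3 power points when site explains 10% of the variance left after baseline. The number of site levels, two or three, cannot be read from the plan.

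**What to change.** Rewrite the Aim 2 paragraph of Section 14:

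- For each outcome, at 1 month (Hypothesis 2a) and at 6 months (Hypothesis 2b), fit a between-arm model with arm, baseline score and performance site as fixed effects, analysing care partners as randomised.
- Report the adjusted arm difference with its 95% confidence interval as the efficacy result, and base the effect size on that difference.
- Keep within-arm paired changes as description only.
- If a rank-based alternative is wanted for skewed scores, make it between-arm as well, for example a Wilcoxon rank-sum test stratified by site (van Elteren).
- Define performance site and reconcile the hospital lists in Sections 3 and 9, so that the randomisation strata are the site levels in the model.
- State what the 1-month visit is counted from: Hypothesis 2a counts from discharge, and Section 4 from the end of the intervention.

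The cost is one rewritten paragraph and the reconciled text. The site term uses one degree of freedom with two sites or two with three. The model needs only arm, site, baseline and follow-up scores, so there are no new data to collect.
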